- Patients treated with radiation therapy on NCI treatment protocols will be asked to provide samples prior to any local or systemic therapy as well as before, during and after their radiation treatment.
- These samples will be tested for the presence of tumor specific DNA mutations and aberrant methylation patterns determined to be present in each patient's tumor by screening of initial biopsy or surgical material.
- Tumor markers specific to each patient, such as tumor specific DNA mutations or aberrant DNA methylation, may provide an individualized method to evaluate disease status and determine prognosis after therapy. Additionally, a number of stool and serum markers will be explored as early indicators of acute and eventual chronic gastrointestinal injury in patients receiving radiotherapy to the abdomen.

Table of Contents

1. Introduction	
1.1 Study Objectives.....	4
1.2 Background and Rationale.....	4
2. Eligibility Assessment and Enrollment.....	9

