1.0 INTRODUCTION

1.1 STUDY OBJECTIVES

1.1.1 Primary Objectives:

- To determine if tumor specific DNA mutations and aberrant DNA methylation found in the tumor of patients treated with definitive intent for gastrointestinal malignancies can be detected in the serum, urine, or stool at the time of diagnosis
- To determine if changes in mutational status at follow-up are associated with disease persistence, recurrence, or survival.
- To determine if pre-treatment, post-treatment, and follow-up measurements of TGF β 1 in the urine and plasma can be used to predict late gastrointestinal toxicity.

1.1.2 Secondary Objectives:

- To determine which biological fluid (serum, urine, or stool) is most highly associated with the detection of tumor specific DNA mutations and tumor specific DNA methylation.
- To determine which biological fluid (serum, urine, or stool) provides the best source of tumor specific DNA to measure at follow-up for association with disease persistence, recurrence, or survival.
- To determine if novel serum, urine, and stool biomarkers obtained at the time of treatment and shortly after treatment can be used to predict the likelihood of chronic gastrointestinal toxicity in patients receiving radiotherapy for gastrointestinal malignancies.
- To determine whether novel serum, urine, and stool markers obtained at the time of treatment and shortly after treatment are influenced by the radiation dose delivered to abdominal organs.

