1.2.2.2 Circulating and excreted nucleic acids as a marker of disease status

Previous studies of DNA mutations and hyper- and hypo-methylation have screened for a variety of markers in the serum or urine of patients, however most have limited the analysis to a few markers in each study, resulting in a significant percentage of patients in whom none of the screened markers were detected. By screening the patient's tumor for mutations and aberrant methylation prior to treatment, it may be possible to select appropriate markers to monitor for each patient. This individualized approach of following markers known to be present may provide a sensitive tumor marker panel specific to each patient's tumor.

In protocol, we hope to evaluate whether we can reliably detect tumor specific mutations and tumor specific epigenetic alterations in the serum, urine, and stool of patients with GI cancers. In addition, we hope to determine if any of these biological specimens is superior for this purpose. Finally we hope to determine if the ability to detect these markers in the biological fluids of patients who have undergone curative therapy for cancer is predictive of failure.

The specific mutations and alterations in nucleic acids to be tested will vary with the primary site and histology of the tumor, based on published frequencies of mutations and aberrantly methylated sequences specific to each histology and tumor site (See Appendix IIA). Each of these mutations has been tested with positive and negative control cell lines in the laboratory of [name] and have previously undergone primer and buffer optimization (Figure 1).

The ability to recover these mutations and aberrations from paraffin embedded tumor sections has also been demonstrated in [name] laboratory. Positive and negative controls have been identified and tested for each of these mutations and methylation patterns (see Appendix IIB). Additional candidate mutations and aberrant DNA methylation markers may be tested in the tumors and specimens of patients in whom none of these are found to be present.

[figure not shown]

Figure 1. PCR products of positive and negative control cell lines and paraffin embedded tissue sections. BxPC3 is a pancreatic cell line known to have wild type ras. MiaPaCa-2 is a cell line known to have the KRM2 k-ras mutation. AsPC1 is a pancreatic cell line known to have the KRM3 k-ras mutation. CFPAC is a pancreatic cell line known to have the KRM4 k-ras mutation.

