2.0 Eligibility Assessment and Enrollment

2.1 ELIGIBILITY CRITERIA

2.1.1 *Inclusion Criteria*

- 2.1.1.1 Age \geq 18 years
- 2.1.1.2 Histologically confirmed carcinoma of the gastrointestinal tract (esophagus, stomach, pancreas, bile duct, rectum)
- 2.1.1.3 Treatment plan includes radiotherapy to the site of the gastrointestinal malignancy on an NCI protocol
- 2.1.1.4 Paraffin embedded tumor tissue from biopsy adequate in amount to perform PCR and methylation specific PCR or willingness to undergo rebiopsy

2.1.2 *Exclusion Criteria*

- 2.1.2.1 Inability to provide informed consent
- 2.1.2.2 Patients who have a history of prior therapeutic radiation
- 2.1.2.3 Patients with evidence of distant metastases on initial staging evaluation
- 2.1.2.4 Patients with other cancers excluding non-melanomatous skin cancers or carcinoma in situ
- 2.1.2.5 Patients who have undergone complete resection of the gastrointestinal malignancy prior to protocol enrollment
- 2.1.2.6 History of inflammatory bowel disease
- 2.1.2.7 History of collagen vascular disease or disease of altered collagen metabolism (end stage renal disease or hepatic fibrosis due to chronic hepatitis)
- 2.1.2.8 History of hypersensitivity to radiation or a history of a disease which results in mucosal or other hypersensitivity to radiation (Ataxiatelangiectasia, Bloom's Syndrome, Human Immunodeficiency Virus, Fanconi anemia, nevoid basal cell carcinoma syndrome, Li-Fraumeni syndrome, and Nijmegen breakage syndrome)
- 2.1.2.9 Inability to return for followup visits
- 2.1.2.10 Patients who have previously received or are currently receiving MDX-101 (ipilimumab).
- 2.1.2.11 Diagnosis of HIV, Hepatitis B, or Hepatitis C

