3.0 STUDY IMPLEMENTATION

3.1 STUDY DESIGN

3.1.1 Overall Trial Design (see Appendix IA)

Patients planned to receive radiotherapy for carcinoma of the esophagus, stomach, pancreas, rectum, or other biliary malignancies as part of their primary therapy will be potential candidates for enrollment on this protocol. This is not a study of an experimental therapy and will be administered in conjunction with protocol therapy for patients receiving radiation as part of the treatment of a gastrointestinal carcinoma. 120 patients will be included from the following sites: 30 patients with esophageal or GE junction cancer, 30 patients with locally advanced biliary malignancies (including pancreas and bile ducts only), 30 patients with resected biliary malignancies (including pancreas and bile ducts only), and 30 patients with rectal cancer.

Serum, plasma, urine, and stool samples will be collected prior to any therapy (surgery excluding biopsy, systemic therapy, or radiotherapy), prior to radiotherapy (if different from "prior to any therapy"), at completion of radiation (within the final five fractions), and at 1, 3, 6, 12, 24, and 36 months follow-up

The Intestinal Permeability Assessment will be performed following protocol sample collection (above) at the following time points: prior to any therapy, prior to radiotherapy (if different than "prior to therapy"), at 1 month follow-up, and at 3 months follow- up.

Tumor tissue obtained at biopsy or resection will be screened for a defined panel of mutations using PCR and abnormal methylation status will be determined by methylation specific PCR. Serum, urine, and stool samples obtained prior to therapeutic intervention will be screened for the same panel of markers. Serum, urine, and stool obtained during treatment and at follow-up will be evaluated for these

same DNA markers and correlated to evidence of gross residual disease on physical examination and follow-up imaging.

Potential serum, plasma, and stool markers of gastrointestinal toxicity will be correlated to validated measures of gastrointestinal toxicity.

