5.4.2 Association between longitudinal measures of TGF β 1 and late gastrointestinal toxicity

We will examine whether levels of TGF β 1 measured in urine and plasma at various timepoints during and after therapy are associated with late gastrointestinal toxicity. Of particular interest will be examining whether changes in TGF β 1 measured over time affect the probability of RTOG ≥ 2 toxicity at 12 months after the completion of radiation therapy. The analysis will be done by relating change in TGF β 1, evaluated by estimating a slope using least-squares regression on each patients repeated follow-up measurements, and the probability of RTOG ≥ 2 at 12 months after completion of therapy using logistic regression. These analyses will be done with and without adjustment for radiation dose to non-target organs (radiation dosimetry). Interest will focus on whether a positive change in TGF β 1 over time (positive slope) is associated with an RTOG ≥ 2 toxicity at 12 months post-therapy. We expect that, on average, approximately 60% of patients will have a RTOG ≥ 2 at 12 months. We also assume that at a minimum of 76 patients of 120 accrued to the study will be alive at 12 months (there is a 95% chance that there will be 76 or more patients will be alive and evaluable at 12 months if the one-year survival/evaluable rate is 70%). Assuming a that 76 patients will be evaluated for toxicity at 12 months and that 50% of estimated slopes are positive, we will have 93% power to detect a difference in the proportion of RTOG ≥ 2 at 12 months of 80% for a positive slope as compared with 40% for a negative or zero slope with a Chi-square test at the 0.05 significance level. A logistic regression analysis treating the estimated slope as a continuous variable should have more power than the Chi-square test.

5.4.3

Analysis of secondary objectives

We will compare the accuracy of DNA mutations and DNA methylation tests in serum, urine, and stool (relative to tumor biopsy) by comparing estimated sensitivities and specificities of the various tests.

We will evaluate which biological fluid provides the best source of tumor specific DNA for association with subsequent disease using logistic regression and Cox proportional hazards models with DNA tests from the different fluids being independent variables in the models.

We will relate novel serum, urine, and stool markers measured during and shortly after treatment to toxicity using logistic regression analysis similar to 5.3.2.

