Appendix IB. Specimen processing and storage

Urine

- **Note: Urine will remain on ice or at 4° Celsius until processed. Time to processing will be minimized.**
- Urine will be collected in a sterile collection cup in the ROB clinic (with the exception of urine collected for the intestinal permeability test which will be brought to the clinic by the patient in the previously provided collection jug).
- Urine will be transported on ice immediately to the laboratory of [name]. [name] for further processing
- Urine collected for the intestinal permeability assessment will be shipped by [name] lab via federal express to Genova diagnostics without further processing.
- Urine for further analyses at NIH will be centrifuged at 1500 x g for 10 minutes at 4° Celsius
- The supernatant will be aliquoted into five 1 mL fractions in 1.5 mL tubes and two 5 mL aliquots and stored at -80° Celsius until use.
- The pellet of urine sediment will be resuspended in 100 uL of sterile PBS and stored at -80° Celsius.

Plasma

- Collect plasma in EDTA containing tubes and place on ice immediately
- Plasma will then be transferred to the laboratory of [name]. [name] for further processing
- Centrifuge at 1000 x g at 4° Celsius for 15 minutes **within 30 minutes of collection**, followed immediately by centrifugation at 10,000 x g at 4° Celsius for 10 minutes
- Aliquot immediately into at least four 500 uL aliquots and store at -80° Celsius

Serum

- Collect blood in serum separator tubes and allow sample to clot at room temperature for 30 minutes
- Serum will then be transferred to the laboratory of [name]. [name] for further processing
- Centrifuge at 1000 x g for 15 minutes
- Remove serum immediately, divide into 1 mL aliquots, and store at -80° Celsius

Stool

- Transport stool immediately to the laboratory of [name], M.D. [name] for further processing
- Stool will immediately be divided into 180-220 mg aliquots, pH tested, and stored at -20° C until further use.

Appendix II A: Specific Tumor Markers To Be Screened In Tumor By Disease Site. Positive Markers Will Then Be Screened In Serum, Urine, And Stool.

Site	Mutation	Aberrant methylation
Esophageal squamous cell carcinoma	p53 (exons 5, 6, 7, 8, 9) ⁸²	p16 ⁸³ MGMT ⁸⁴ E-cadherin ⁸⁴
Gastric and esophageal adenocarcinoma	p53 (exons 5, 6, 7, 8, 9) ⁸⁵	APC ^{14, 86, 87} E-cadherin ^{13, 14, 86, 88} hMLH1 ¹⁴ TIMP3 ¹⁴ p16 ^{13, 88}

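### Section 5.4.3 plans specificity of the fluid DNA tests, but one of the plan's two fluid-testing rules leaves no tumor-negative gene to estimate it from

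*Combined protocol and SAP*

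**What the plan says.** Section 5.4.3 takes tumor biopsy as the reference and compares the three fluids by "comparing estimated sensitivities and specificities of the various tests". It does not say whether the unit is a gene, a single assay or a patient.

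Two rules decide which markers reach a fluid assay:

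- **Full panel.** Section 3.1.1 screens the tumor for a defined panel and says that pre-treatment serum, urine and stool "will be screened for the same panel of markers".
- **Tumor-positive markers.** The title of Appendix IIA lists the markers to be screened in tumor and adds: "Positive Markers Will Then Be Screened In Serum, Urine, And Stool". The Design part of the Precis says the samples are tested for "tumor specific DNA mutations and aberrant methylation patterns determined to be present in each" patient's tumor. The rationale in 1.2.2.2 points the same way, describing an individualized approach of "following markers known to be present".

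No section reconciles the two.

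**The concern.** Specificity against tumor biopsy needs markers that are absent from the tumor and were nevertheless tested in the fluid. The tumor-positive rule removes exactly those. If the laboratory works from Appendix IIA, one of the two accuracy measures planned for choosing between fluids cannot be computed. Nor can it be recovered from the data afterwards, because the tumor result will already have decided which fluid tests exist. The question therefore has to be settled before the assay work.

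**Working it through.** The plan gives no sample size or precision for 5.4.3, so there is no stated figure to reproduce. The check is a count.

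**Inputs.** Four groups of 30, 120 in all (3.1.1). Panels from Appendix IIA. Tumor prevalences p from the Tumor Marker Prevalence appendix (headed IIB on its pages, IIC in the table of contents).

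**Definition.** Specificity denominator = number of patient-marker pairs that are tumor-negative *and* tested in the fluid.

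**Tumor-positive rule, gene as unit.** Tumor-negative panel genes tested = 0 for every gene, fluid and site, so specificity = 0/0. There are two partial exceptions:

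- If all assays of a positive gene are rerun in fluid (K-ras variants, p53 exons), some single-assay negatives arise within that gene.
- Section 1.2.2.2 allows additional candidate markers for patients with no panel marker. These lie outside the panel and concern few patients.

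Neither supplies specificity for the panel genes.

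**Full-panel rule.** Expected tumor-negative patients per 30 of one tumor type = 30 × (1 − p), assuming all 30 have a tumor result:

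| Tumor type | Tumor-negative patients per 30 |
|---|---|
| Esophageal adenocarcinoma | p53 30 × 0.05 = 1.5; APC and E-cadherin 30 × 0.30 = 9 each; TIMP3 30 × 0.44 = 13.2; p16 15–16.5; hMLH1 30 × 0.88 = 26.4 |
| Pancreas | K-ras 1.5–7.5; ppENK 3–6; p53 7.5–15; DPC4 13.5–16.5; p16 14.4–25.5 |
| Rectal (colorectal-cancer figures) | vimentin 5.1–14.1; p53, APC, K-ras 18–21 each; p16 22.5; p14 26.1 |

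The squamous p53 and bile duct K-ras prevalences are so wide (10–85% and 21–100%) that their counts run from 4.5 to 27 and from 0 to 23.7. No planned group is purely pancreatic: both biliary groups mix pancreas and bile duct, and the esophageal group may mix histologies. The table is therefore per 30 of a tumor type, not per planned group.

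**Precision.** With no false positive, the exact 95% lower limit for specificity is 0.025^(1/n): n = 2 gives 15.8%, n = 9 gives 66.4%, n = 26 gives 86.8%.

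**Pooled count per fluid.** Sum of (1 − p) per patient: squamous 1.50–2.25; adenocarcinoma 2.47–2.52; pancreas 1.33–2.35; bile duct 0.90–2.30 (joint p16/p14 figure counted once); rectal 3.59–4.19.

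- Low: 30 × 1.50 + 60 × 0.90 + 30 × 3.59 = 206.7
- High: 30 × 2.52 + 60 × 2.35 + 30 × 4.19 = 342.3
- Three fluids: 620 to 1,027 gene-level tests

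With the serrated-adenoma figures for rectal p16 and p14, the rectal low end is 2.80 and the pooled low end is 45 + 54 + 84 = 183. These counts size the laboratory work. They do not measure precision, because markers within a patient are not independent observations.

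**Patient as unit.** Under the independence assumption in 5.4.1, 30 × ∏(1 − p) summed over the groups gives about 0.7 to 8.9 of 120 patients negative on every marker. Using the appendix's joint figure of 75% for at least one of K-ras, p53 and APC in rectal cancer, the upper value is about 8.1. Patient-level specificity is thus nearly empty even under full-panel testing.

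**The case against.** The best defense is that 3.1.1 is the design section and already supports 5.4.3. The opposing texts are a Precis bullet, an appendix title and background rationale. The Precis does not say that *only* present markers are tested, and 1.2.2.2 can be read as being about monitoring. One could then have the full panel at baseline and positive markers at follow-up. This makes the loss conditional, and that much stands. It does not remove the conflict: the Precis applies its present-in-tumor rule to samples that include those taken before any therapy, and the tumor analysis text (3.2.1.1.3) refers the reader to Appendix II A and B. Nothing says that 3.1.1 prevails.

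A second defense is that little is lost. The secondary objective in 1.1.2 asks which fluid is "most highly associated with the detection of tumor specific DNA mutations and tumor specific DNA methylation", and paired sensitivity answers much of that under either rule. This stands and limits the weight of the point.

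Third, section 1.2.2.2 reports that "Positive and negative controls have been identified and tested for each of these mutations and methylation patterns". Those controls speak to assay validity. They do not measure false positives in patients' serum, urine and stool.

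Fourth, per-marker significance tests between fluids would be of little use at these counts. An exact two-sided McNemar test needs at least 6 discordant pairs, all in one direction (2 × 0.5^6 = 0.031; with 5 it is 0.063). That is correct, and the remedy below therefore keeps per-marker results descriptive.

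**Conclusion.** The point holds in conditional form. Under Appendix IIA and the Precis, gene-level specificity for the panel is 0/0; under 3.1.1 it can be estimated per marker at baseline, poorly for some markers. The document states both rules and no unit.

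A reader might infer that the planned specificity analysis is impossible, or that the fluid comparison fails. The documents support neither: 3.1.1 states a rule under which specificity exists, and sensitivity is available under both. Nor can patients in complete response supply the missing negatives, since 5.4.3 names tumor biopsy as the reference and every participant has confirmed carcinoma.

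The effect is confined to one accuracy measure in a secondary analysis. It is worth correcting because a stated rule defeats a stated analysis and the correction is cheap if made in time. The counts rest on the plan's literature prevalences and on every patient having a tumor result. Each biliary-group patient without one removes about 0.9 to 2.4 tumor-negative pairs per fluid. The entry criterion requiring tissue "adequate in amount to perform PCR and methylation specific PCR or willingness to undergo rebiopsy" and the search for prior specimens (3.2.1.1.1) limit how often that happens.

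**What to change.** Before assays are run, reconcile the Precis, 3.1.1 and Appendix IIA to one fluid-testing rule and make 5.4.3 match it. Both options below fit parts of the current text, and the choice is the sponsor's.

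- **(a) Full panel in baseline fluids.** State in 5.4.3 whether the unit is the gene or the single assay. Report per-marker specificity descriptively with exact confidence intervals. Make any between-fluid comparison on pooled markers with a paired method that clusters by patient. If 3.1.1 is the intended rule, this is wording only. If Appendix IIA is, it adds about 620 to 1,030 gene-level baseline tests on samples already collected. The number of individual assays would be higher, because Appendix IIA lists 3 to 5 p53 exons, 4 or 5 K-ras assays and 4 DPC4 exons, depending on site.
- **(b) Tumor-positive markers only.** Delete specificity from 5.4.3 and claim only paired sensitivity. This is wording only, at the price of one accuracy measure.

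Neither option adds a patient procedure.

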For the first primary objective, tumor-specific DNA mutation markers will be collected at baseline (before any therapy and before radiation begins) at completion of radiation therapy and at 1, 3, 6, 12, 24, and 36 months of follow-up. Of interest is examining whether changes in the average mutation frequency (of the disease-specific mutations given in Appendix IIA) effects response to therapy, overall survival, and disease-free survival among complete responders to all therapy. Various analyses will be done to address with objective. These analyses will be done separately by tumor type as well as combined over tumor type (assuming that the relationship between marker changes and disease outcome do not vary across tumor type). First, we will examine the relationship between changes in mutational status over time and survival with Cox proportional hazards models. The relationship between changes in mutational status over time and complete response will be estimated using logistic regression analysis. One key primary analysis will be to examine whether having all tumor-specific markers being negative at 3 months after radiation therapy ends is associated with long-term survival. Note that based on the tumor marker prevalences in the literature (see Appendix IIC) and an assumption that marker prevalence is independent across the various markers, the probability of having at least one mutation which is positive before treatment is very high. Our sample size calculations assume that 50% of patients will have all tumor-specific markers negative 3 months after radiation therapy ends. Based on conducting a two-sided log-rank test at the 0.05 significance level with a total enrollment of 120 patients, we would have 89% power to detect a difference between 35% overall 2-year survival in the positive marker group and 65% overall 2-year survival in the negative marker group. We will have power only to detect large differences for the tumor-specific analyses. With 30 patients in each group (15 patients in the positive and negative groups, respectively), we would have 83% power to detect a difference in 2 year survival of between 80% in the marker negative group and 20% in the marker positive group using a log-rank test at the 0.05 significance level. The above sample size calculation depends heavily on the assumption that 50% of patients will have all tumor-specific markers negative at 3 months. The power may be severely diminished if this proportion deviates too much from 50%. Thus, alternative similar analyses will also be conducted. For example, we will compare survival by whether the change in tumor-specific marker frequency from

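### The best-fluid objective is matched to models whose natural reading gives each fluid's added value, not its value as a single source, and no criterion for calling a fluid best is stated

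*Combined protocol and SAP*

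**What the plan says.** Section 1.1.2 sets two separate fluid objectives. One concerns detection of tumour DNA. The other is the one at issue here: "To determine which biological fluid (serum, urine, or stool) provides the best source of tumor specific DNA to measure at follow-up", judged by association with persistence, recurrence or survival.

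Section 5.4.3 gives the second objective one sentence of method. The best fluid will be evaluated by logistic and Cox models, "with DNA tests from the different fluids being independent variables in the models". It names no measure or rule for calling a fluid best: no AUC, C-index, likelihood comparison, contrast of coefficients or confidence interval. The time point and the coding of the test are also not given for this analysis.

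The same section compares the fluids "by comparing estimated sensitivities and specificities of the various tests", but relative to tumour biopsy. That serves the detection objective and does not fill the gap.

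The title of Appendix IIA states which markers are tested in the fluids: "Positive Markers Will Then Be Screened In Serum, Urine, And Stool".

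**The concern.** The three tests look for the same patient-specific markers in the same patient, so their results should be positively correlated. In a model holding all three, the coefficient for stool (say) compares patients with different stool results but the same serum and urine results. That answers whether stool is worth adding to serum and urine. The objective asks which fluid to use as the source. These are different quantities at any sample size.

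There is also an inferential cost. Correlated covariates share the signal and inflate each other's standard errors, so a fluid that predicts well alone may appear with a small, non-significant or even negative coefficient. With no stated criterion for best, a reader of the results table would probably fall back on the p-values and could discard a good fluid or prefer a poor one.

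**Working it through.** **Anchor: the plan's own survival effect.** The plan gives no figure for the fluid comparison, so the effect size is taken from the key primary analysis in Section 5.4.1: a "two-sided log-rank test at the 0.05 significance level with a total enrollment of 120 patients", with "89% power to detect a difference between 35% overall 2-year survival in the positive marker group and 65% overall 2-year survival" in the negative group, assuming that "50% of patients will have all tumor-specific markers negative 3 months after radiation therapy ends".

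- Hazard ratio under exponential survival: ln 0.35 / ln 0.65 = 2.44.
- Deaths by 24 months: 60 × 0.65 + 60 × 0.35 = 60.
- Freedman power: Φ(√60 × (2.44 − 1)/(2.44 + 1) − 1.96) = Φ(1.28) = 89.9%, against the stated 89%.
- The same formula for 15 versus 15 patients (20% versus 80%; hazard ratio 7.21; 15 deaths) gives 83.4%, against the stated 83%.

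The plan's figures are reproduced, so a hazard ratio of 2.44 with 120 patients is a fair basis.

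**Standard errors.** For three tests with common correlation r, the variance inflation is (1 + r)/[(1 − r)(1 + 2r)], and the standard error multiplier is its square root.

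- r = 0.3: √(1.3/(0.7 × 1.6)) = 1.08
- r = 0.5: √(1.5/(0.5 × 2.0)) = 1.22
- r = 0.7: √(1.7/(0.3 × 2.4)) = 1.54

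**Simulation, survival.** There were 1000 trials per setting, with 120 patients followed for 3 years (the follow-up in Section 3.6.4). A latent tumour-DNA status is positive in 50% and carries the hazard ratio of 2.44. Each fluid test reads that status with sensitivity = specificity = a, with independent errors. The correlation between fluids i and j is then (2aᵢ − 1)(2aⱼ − 1); for example, 0.95 and 0.85 give 0.9 × 0.7 = 0.63. The documents give neither accuracies nor correlations, so all values of a are assumptions.

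| Assumed accuracies | Correlation | Best fluid significant: alone / joint | Best fluid ranked first: single-fluid likelihood / joint coefficient |
|---|---|---|---|
| 0.95, 0.85, 0.85 | 0.48-0.63 | 93% / 41% | 71% / 70% |
| 0.95, 0.90, 0.90 | 0.64-0.72 | 94% / 22% | 53% / 53% |
| 0.90, 0.70, 0.70 | 0.16-0.32 | 87% / 69% | 83% / 82% |

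In the first two settings the best fluid's mean log hazard ratio fell from 0.80 to 0.61 and from 0.81 to 0.50 on joint entry. Across all settings run, at least one fluid had a negative joint coefficient in 52-69% of trials. With three equally good fluids (0.95 each, correlation about 0.81), a given fluid was significant alone in about 93% of trials and jointly in 11%.

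**Simulation, response.** With logistic models, 120 patients and assumed accuracies, the best fluid was significant in 87% of trials alone against 33% jointly at correlations of about 0.5-0.6, and in 74% against 53% at about 0.2-0.3.

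**Shared errors.** If two fluids tend to be wrong in the same patients, each is redundant given the other, and a weaker fluid with separate errors can look stronger in the joint model. In one assumed strong-effect setting, with correlation 0.87 between two fluids, the best fluid was jointly significant in 20% of trials and the weakest in 57%. The best fluid came first in 24% of trials by joint z statistic and in 57% by AUC. This shows that the reversal can happen, not how often it would.

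**The case against.** Five points can be made for the plan.

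- **Joint entry is not explicit.** A reader might take Section 5.4.3 to state a single model with all three fluids. It does not. The plural is explained by there being two model types, but one model per fluid is not excluded. This stands, and it is a reason to settle the wording.
- **The joint model can still rank fluids.** A reader might infer that correlated tests cancel and that the model cannot identify the best source. That is not supported: the signal is shared, not cancelled, and ranking by joint coefficient matched single-fluid ranking to within about one percentage point when errors were independent. This stands. What is lost is the inference on individual fluids, and the plan does not say that it would rank by coefficient.
- **Significance against no effect does not separate fluids.** This stands, and it applies to single-fluid p-values too: three equally good fluids would nearly all be significant alone. A direct paired comparison is therefore needed, not three separate p-values.
- **The correlations may be lower.** Section 1.2.2.1 describes stool DNA as coming from cells shed into the lumen, a different route from circulating DNA. At correlations of about 0.2-0.3 the dilution is much smaller, though still present.
- **Missing samples.** A reader might hold it against the joint model that it loses patients lacking any one fluid. A paired comparison is limited to the same patients, so this does not favour either approach.

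**Conclusion.** The concern holds in a limited form. On its natural reading, the planned analysis estimates each fluid's added value given the other two, while the objective asks for its value as a single source. On either reading, the plan gives no criterion for best. The mismatch of quantities does not depend on any assumption.

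The size does. With assumed accuracies, the best fluid is significant in about 87-94% of trials alone against 22-41% jointly at correlations of about 0.5-0.7, and in 74-87% against 53-69% at about 0.2-0.3. The possibility that joint significance favours the wrong fluid rests on one assumed setting with shared errors.

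The documents do not support saying that the planned model is uninformative. Nor do the calculations show that a per-fluid analysis of 120 patients will reliably pick the winner: the single-fluid survival models ranked the best fluid first in only 53-83% of trials in the tabulated settings. This is a secondary objective of a pilot study, so the impact is moderate, but choosing a fluid is what the objective is for.

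**What to change.** Reword the best-fluid sentence in Section 5.4.3 to prespecify the following.

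1. One logistic model (response) and one Cox model (survival) per fluid, all fitted on the same patients, namely those with all three fluids at the chosen time point.
2. The criterion for best: AUC for response and C-index for survival, with pairwise differences between fluids and paired bootstrap confidence intervals. If the intervals do not separate the fluids, report that.
3. The joint model kept for one question only: whether a second fluid adds information to the best one.
4. The time point and the coding of the test (for example any marker positive, or proportion positive).

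The cost is SAP wording and a few more models, with no new samples or data. The downside is that the paired comparison is restricted to patients with all three fluids, as the joint model already is. The number of such patients should be reported.
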